[figure not shown]

**A Research on the Ovarian Function Detection and Protection in
Fertility Preservation Surgery for Ovarian Malignancy**

2019.02.01

Study objectives The primary objective of this study is to identify whether applying GnRHa on patients with ovarian malignancy for fertility preservation surgery preoperatively and postoperatively has a different outcome. By comparing the physical and hormone indexes in the control group and experimental group, we plan to find out the effect of GnRHa.

Trial design This is a prospective interventional trial. After signing of informed consent, the electronic medical data of patients with ovarian malignancy will be collected in this study. 20 patients will be enrolled in this trial. They will be randomized into the control group and the experimental group as to receive GnRHa for fertility preservation surgery preoperatively and postoperatively. We plan to investigate into the effect of GnRHa by monitoring the physical ovarian change and the six hormone indexes in the two different groups.

Sample size The planned sample size was based on data from a previous study, in which the standard deviation was 5. We assumed an one-tailed α error of 0.05 and a sampling error of 1.0. We propose to enroll 24 participants including 12 patients in the control group and the others in the experimental group, and allow for a dropout rate of 10% for an effective sample size of 20.

Inclusion criteria

1. Volunteer to participate in the study with informed consent;
2. Females aged 10-90 who are confirmed with ovarian malignancy and are willing to receive fertility preservation surgery.

Exclusion criteria

1. Suspected or identified as other tumors of genital tract;
2. History of hyperparathyroidism, infectious diseases (tuberculosis, AIDS), autoimmune diseases, or digestive system diseases (malabsorption, crohn disease and dysentery);
3. Other diseases or heavy injuries that will interfere with the results;
4. Simultaneous participation in another clinical study with investigational medicinal product(s) or researcher thinks the subjects are not suitable for this trial.

Withdrawal Subjects must be withdrawn from the study when one of the following criteria occurs:

1. At their own request. At any time during the study and without giving reasons, a subject may decline to participate further. The subject will not suffer any disadvantages as a result;
2. In the investigator's opinion, continuation of the study treatment would be harmful to the subject's health;
3. Obvious non-compliance;
4. Lost to follow-up;
5. Pregnancy;
6. Other medical or surgical treatments of endometrial carcinoma.

Safety assessments

Safety will be assessed by renal and liver function test, electrolyte, routine blood test. Other indicators are detected during the operation and rehabilitation period. The occurrence of any adverse events in participants will be recorded in the case report forms during each patient visit. We will withdraw patients who have severe adverse events, as it is unsafe for them to continue the trial. Meanwhile, we will give them relevant medical care and follow them up until the reaction has terminated.

Statistic analysis

Before the enrollment of participants, patients' medical data will be collected and analyzed to evaluate whether they are suitable for this trial. With their informed consent, they will be randomized into the control group and the experimental group. The situation of the two group will be almost the same considering the average age, the average BMI, the average grading evaluation. The fertility preservation surgery means the ovary affected by cancerous cell is resected when the other is preserved. If the other side was already resected, the ovarian tumor on the affected side will be removed. Before and after the operation, patients in the control group will receive placebos when the experimental group will receive GnRH_a. The physical ovarian volume, six hormone indexes, AMH and the ovulating period will be monitored and compared by chi-square analysis in SPSS 17.0.

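### The plan gives two enrolment targets, 20 and 24; stopping at 20 would leave about 18 evaluable patients, below the 20 it relies on

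*Combined protocol and SAP*

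**What the plan says.** Two adjoining sections of the combined protocol and SAP give a number to be enrolled.

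- **Trial design:** "20 patients will be enrolled in this trial". The next sentence has these patients randomised to control or experimental treatment, so the 20 are patients entering the trial, not patients left at analysis.
- **Sample size:** "We propose to enroll 24 participants including 12 patients in the control group and the others in the experimental group", that is, 12 and 12. The same sentence goes on to "allow for a dropout rate of 10% for an effective sample size of 20".

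Only the Sample size section gives arm sizes or a dropout allowance. The document has no amendment history that would mark either figure as superseded, and no later section returns to the number.

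**The concern.** An enrolment target has to be one number. Here a reader of Trial design would close recruitment at 20, and a reader of Sample size would close it at 24. The gap is 4 patients, or 4/24 = 17% of the larger figure.

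The lower figure also conflicts with the plan's own reasoning. The dropout allowance exists so that 20 patients remain after losses. If only 20 enter, a single loss puts the trial below that number. Losses are likely: the Withdrawal section requires withdrawal for non-compliance, loss to follow-up and pregnancy, among other grounds, and the Safety assessments section adds severe adverse events.

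Reporting is affected too. If 20 are enrolled, the trial is either complete or 4 short; if 24 are enrolled, it is either complete or 4 over. Each description could cite the protocol.

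**Working it through.** **Inputs**

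| Input | Value | Source |
|---|---|---|
| Enrolled, first figure | 20 | Trial design |
| Enrolled, second figure | 24 (12 + 12) | Sample size |
| Dropout | 10% | Sample size |
| Effective (evaluable) size | 20 | Sample size |
| Standard deviation | 5 | Sample size |

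**1. Reproduce the plan's 24.** The number to enrol is n / (1 − d).

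- In total: 20 / 0.9 = 22.2, rounded up to 23.
- Per arm: 10 / 0.9 = 11.1, rounded up to 12, so 2 × 12 = 24.

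The stated 24 follows from 20 evaluable and 10% dropout when rounding is done within arms.

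**2. Expected evaluable number under each target.** This is N × (1 − d).

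- Enrol 20: 20 × 0.9 = 18, about 9 per arm if allocation is equal. This is 2 short of 20.
- Enrol 24: 24 × 0.9 = 21.6. This covers 20.

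**3. Chance of reaching the effective size.** Assume each patient is retained independently with probability 0.9.

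- Enrol 20: all must stay, so 0.9^20 = 0.122, about 12%.
- Enrol 24: P(at least 20 of 24 retained) = 0.915, about 91%.
- Enrol 24 and require at least 10 in each arm: P(at least 10 of 12) = 0.282 + 0.377 + 0.230 = 0.889 for one arm, and 0.889² = 0.79 for both.

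**4. Effect on precision.** The two-sided 95% half-width for a difference in means is t × SD × √(2/n per arm), with SD 5.

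- 9 per arm (16 degrees of freedom): 2.120 × 5 × √(2/9) = 5.0.
- 10 per arm (18 degrees of freedom): 2.101 × 5 × √(2/10) = 4.7.

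The ratio is 5.00 / 4.70 = 1.06, so the interval is about 6% wider. The two-sided 95% interval is a choice made here; the plan specifies a one-tailed α of 0.05. The plan attaches no endpoint or unit to the SD, so these widths have no clinical scale and only their ratio is informative.

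**The case against.** The strongest reply is that this is a drafting slip of little consequence. The 20 in Trial design equals the effective size in the next section, so it is probably the analysis number written as the enrolment number. The arm sizes and dropout allowance appear only alongside 24, so a careful site would probably follow 24. If 20 were followed, the interval would widen by only about 6%, and at either size the half-width is close to one standard deviation.

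Much of this is fair. The slip is the likeliest explanation, the precision loss is small, and the documents do not say how recruitment will be closed, so stopping at 20 is a risk and not a certainty. But the sentence says enrolled and the following one says randomised, so the charitable reading means that the sentence is wrong, not that it is harmless.

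A second reply is that 20 is itself unsupported, so falling from 20 to 18 matters little. The inputs are "The planned sample size was based on data from a previous study, in which the standard deviation was 5" and "We assumed an one-tailed α error of 0.05 and a sampling error of 1.0". A single-mean precision formula with these gives (1.645 × 5 / 1.0)² = 67.6, or 68 patients, not 20. That stands as a separate problem, and making the enrolment figures agree does not answer it. It does not remove this one either: a rederived sample size would still need a single enrolment figure.

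It is also true that 24 does not guarantee 10 evaluable per arm. On the independence assumption that fails about 21% of the time (1 − 0.79).

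**Conclusion.** The concern holds. The protocol states two incompatible enrolment targets, and the lower one is not expected to deliver the effective size the plan relies on: 18 against 20, with a 12% chance of reaching 20, compared with about 91% if 24 are enrolled. The expected counts rest only on the plan's 10% dropout rate. The probabilities also assume independent losses, and the per-arm figures assume equal allocation.

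The inconsistency needs correcting because it concerns the figure that defines complete recruitment, not because two patients would change a conclusion. Of the two figures, 24 is the one that agrees with the plan's dropout allowance. Nothing here endorses 20 evaluable patients as sufficient for the trial's question.

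**What to change.** In Trial design, replace the sentence giving 20 with wording such as: *24 patients will be enrolled and randomised, 12 per arm. With 10% dropout, 21.6 are expected to be evaluable (24 × 0.9), against an effective sample size of 20.* Use 24 as the only enrolment figure throughout, and use 20 only for the number needed at analysis. Naming both enrolment and randomisation makes clear that the 24 are counted at entry.

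The cost is one sentence of protocol text and no patients beyond the 24 already proposed. If the effective size is later rederived, recompute the enrolment figure from it in the same way and state it identically in both sections.

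### Ovarian volume is not limited to the preserved ovary or tied to a reference time, so a change from the pre-treatment scan can include the tissue removed at surgery

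*Combined protocol and SAP*

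**What the plan says.** The Trial design section states how the objective will be answered: "We plan to investigate into the effect of GnRHa by monitoring the physical ovarian change and the six hormone indexes in the two different groups". The Statistic analysis section lists the measures again, with two additions: "The physical ovarian volume, six hormone indexes, AMH and the ovulating period will be monitored and compared".

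The same section describes two operations. In the usual case, "The fertility preservation surgery means the ovary affected by cancerous cell is resected when the other is preserved". In the other, "If the other side was already resected, the ovarian tumor on the affected side will be removed". On treatment timing it says: "Before and after the operation, patients in the control group will receive placebos when the experimental group will receive GnRH_a".

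Allocation is by randomisation, and the factors on which the groups are expected to be alike are given as follows: "The situation of the two group will be almost the same considering the average age, the average BMI, the average grading evaluation". Type of operation and tumour size are not among them.

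The documents do not say whether ovarian volume is total or per ovary, which ovary is read, which scan is the reference, or when follow-up volume is taken. They set out no adjustment for type of operation.

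**The concern.** The plan's own word for the physical measure is change, and a change needs a starting value. Because treatment begins before surgery, the only starting value free of treatment is a preoperative one. Eligibility requires confirmed ovarian malignancy, so that scan shows an ovary with a tumour in it. Between that scan and any postoperative one, an ovary or a tumour has been taken out.

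If the change is computed over that interval without restricting it to the ovary that is kept, it mixes two quantities: what happened to the preserved ovary, which is the question, and how much tissue was removed, which is not. With so few patients, patient-to-patient variation in the second could outweigh any drug effect on the first, or create a difference between arms by chance.

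**Working it through.** **Step 1. What a change contains under each reading.** Let K0 and K1 be the volume of preserved ovarian tissue before the first dose and at follow-up. Let T be the volume that surgery removes, as it stood before the first dose.

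- Two ovaries, preserved ovary read alone: change = K1 − K0. No resected tissue enters.
- Two ovaries, total volume: change = K1 − (K0 + T) = (K1 − K0) − T.
- Two ovaries, affected side: change = 0 − T, which says nothing about the preserved ovary.
- Single ovary: the measured ovary is the operated one, so change = (K1 − K0) − T. This cannot be avoided if the preoperative scan is the reference.

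After surgery only the preserved ovary or ovarian tissue is left. T therefore enters only through the preoperative value that is subtracted; the follow-up value does not contain it.

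**Step 2. Bias or noise.** T is fixed before the first dose, so under randomisation it has the same expectation in both arms and cancels on average. A simulation with 10 per arm, a true effect of 5, a kept-ovary SD of 5 and a resected-volume SD of 0, 10, 20 or 50 gave mean arm differences of 5.0, 4.9, 4.9 and 5.1. The SD of that difference rose from 2.2 to 5.0, 9.3 and 22.5. One caveat: if the reference scan came after preoperative dosing had begun, any early drug effect on volume would be mixed with what is later resected. The plan does not exclude that.

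**Step 3. How large T might be.** The documents give no volumes. Assume a normal ovary of 7 mL and a roughly spherical tumour of diameter d, with volume π/6 × d³.

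- d = 5 cm: 65 mL, a share of 65/(65 + 7) = 90%
- d = 8 cm: 268 mL, a share of 97.5%
- d = 15 cm: 1,767 mL, a share of 99.6%

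**Step 4. Precision.** The effective sample of 20 in the Sample size section gives 10 per arm. The 95% half-width for a difference in mean change is t(0.975, 18) × SD × √(2/10) = 2.101 × 0.447 × SD = 0.940 × SD.

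- Preserved ovary alone, assumed SD 2 to 5 mL: 1.9 to 4.7 mL
- Change including resected tissue, assumed SD 50 mL: 47 mL
- The same, assumed SD 400 mL: 376 mL

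**Step 5. Power.** Assume a drug effect of 5 and a kept-ovary SD of 5 in the same unit, with resected volume independent of arm and having SD r. The plan does quote an SD of 5, but names neither variable nor unit, so its use here is only illustrative. With the plan's one-tailed 0.05 and the normal approximation, power = Φ(5 / (√(25 + r²) × √0.2) − 1.645).

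| r | SD of change | SE of arm difference | Power |
|---|---|---|---|
| 0 (preserved ovary only) | 5.0 | 2.2 | 72% |
| 5 | 7.1 | 3.2 | 47% |
| 10 | 11.2 | 5.0 | 26% |
| 20 | 20.6 | 9.2 | 14% |
| 50 | 50.2 | 22.5 | 8% |

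The plan states no figure for ovarian volume, so there is none to reproduce.

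**The case against.** The strongest reply is that the plan never says change is calculated from before to after the operation, nor that volume is total. The wording about before and after surgery concerns when drug or placebo is given, not when volume is measured. That stands: the reading across surgery is an inference from the word change together with the treatment timing. What the documents do establish is that nothing rules it out.

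A second reply is that in two-ovary patients the preserved ovary can be read alone, and its volume contains no resected tissue. That also stands. A reader might infer that volume is dominated by resection whichever operation is done. The documents do not support this; it is unavoidable only in single-ovary patients with a preoperative reference, and their expected number is not given.

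A third reply is that randomisation protects the comparison. It does so against systematic bias. A reader might conclude that the measure would show only resection and nothing of GnRHa, or that a real effect would be invisible. Neither follows for total volume or for single-ovary change: the expected arm difference still carries the drug effect, and the loss is of precision. Randomisation does not, however, prevent chance imbalance in one trial of about 20 patients, and neither tumour size nor type of operation is among the named balance factors.

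Finally, a reader might extend the point to hormone-secreting tumours distorting the hormone indexes and AMH. The documents do not mention such tumours or how often they would occur, so that extension is not made here.

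**Conclusion.** The point holds as a gap in the outcome definition that costs precision. The plan judges GnRHa partly by ovarian change and volume, around operations that all remove tissue, without restricting the measure to the preserved ovary or fixing a reference time. A change from the pre-treatment scan would include tumour removal in every single-ovary patient, and in two-ovary patients whenever total or affected-side volume is used.

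The size of the loss is conditional. The contrast between a half-width of 1.9 to 4.7 mL and one of 47 to 376 mL, and the fall in power from 72% to between 47% and 8%, follow directly from the assumed volumes, SDs and effect, and from the reading that resected tissue enters the change. If the investigators already intend to read only the preserved ovary in two-ovary patients, the loss is confined to single-ovary patients. Volume is also only one of several measures, alongside the hormone indexes, AMH and the ovulating period. The direction is not in doubt: resected volume that varies between patients can only add noise to a change that includes it, if it is unrelated to how the preserved ovary responds.

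**What to change.** Define the physical outcome as the volume of the preserved ovary at a stated follow-up time, and compare follow-up volume between arms.

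- **Two-ovary patients:** read the same ovary before the first dose and use that volume as a covariate.
- **Single-ovary patients:** use the follow-up volume only, with no change from the tumour-bearing scan.
- **One model for all:** regress follow-up volume on arm, an indicator for type of operation, and baseline volume, with the baseline set to a constant in single-ovary patients. The indicator absorbs the constant, so the baseline slope is estimated from two-ovary patients alone.
- **Hormone indexes and AMH:** compare follow-up values between arms adjusted for the pre-dose value, rather than the raw change across surgery.

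The cost is a short paragraph in the Trial design and Statistic analysis sections and per-ovary reading of the scans. Single-ovary patients contribute no baseline volume, and their follow-up volume will still vary with how much tissue was left. The model spends one or two degrees of freedom: with 20 patients, two extra terms reduce 18 to 16, which moves the 95% critical value from 2.101 to 2.120, about 1%. Changing the statistical test or the sample size would not by itself resolve this point.

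### The effective sample size of 20 does not follow from SD 5, one-tailed α 0.05 and a sampling error of 1.0; 10 per arm gives a margin of about 3.9 on the between-group difference

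*Combined protocol and SAP*

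**What the plan says.** The Sample size section states: "The planned sample size was based on data from a previous study, in which the standard deviation was 5". The next sentence adds the other two inputs: "We assumed an one-tailed α error of 0.05 and a sampling error of 1.0". The size follows directly: "We propose to enroll 24 participants including 12 patients in the control group and the others in the experimental group", and the sentence goes on to "allow for a dropout rate of 10% for an effective sample size of 20".

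The section gives no formula, power or target difference. It does not name the outcome or unit that the SD belongs to, and it does not say what sampling error means or which estimate it applies to.

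Study objectives makes the question a two-group one: the effect of GnRHa is to be found "By comparing the physical and hormone indexes in the control group and experimental group". The Statistic analysis section lists the outcomes: "The physical ovarian volume, six hormone indexes, AMH and the ovulating period will be monitored and compared". That is nine measures (volume, six hormones, AMH, ovulating period).

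Trial design gives a different enrolment figure: "20 patients will be enrolled in this trial".

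**The concern.** A size calculation should let a reader go from the inputs to the number. Here an SD of 5 and a tolerance of 1.0 is a demanding ratio for 20 patients in two arms, so the result looked too small on any usual definition.

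The paragraph is the plan's sole support for its size. A reader who takes the 1.0 at face value will expect far more precision on the treatment comparison than the trial can give, and could read a null result as excluding effects that it cannot resolve.

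**Working it through.** **Inputs (Sample size section).** SD = 5; α = 0.05 one-tailed, so z = 1.645; E = 1.0; 24 enrolled, 12 per arm; 10% dropout; effective size 20, so 10 per arm.

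**The dropout step reproduces.** 10/0.9 = 11.1, rounded up to 12 per arm, or 24 in total. The fault lies in the derivation of 20.

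**Reading 1: E is a margin of error (z-based).**
- One mean: n = (z·SD/E)² = (1.645 × 5/1)² = 67.6, so 68. Applied to each arm's mean, this is 68 per arm (136).
- Difference between arms: n per arm = 2(z·SD/E)² = 135.3, so 136 per arm (272). With t quantiles it is 137 per arm (274).

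**Reading 2: E is a standard error.** α then plays no part.
- One mean: n = (SD/E)² = 25. Applied to each arm's mean, this is 25 per arm (50).
- Difference: n per arm = 2(SD/E)² = 50 (100 in total).

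**Reading 3: E is a difference to be detected.** This needs a power, and none is stated. Assuming 80%, one-tailed, it takes 310 per arm. At 10 per arm the t-test power for a difference of 1.0 is about 0.11.

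**Near-matches that depart from the stated inputs.**

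| Reading | Result | What it gives up |
|---|---|---|
| 5 as a variance, two-sided α, one mean | 1.96² × 5 = 19.2, so 20 | the stated SD, the one-tailed α, the two-arm comparison |
| 5 as a variance, one-tailed α, one mean | 1.645² × 5 = 13.5, so 14 | the stated SD; does not give 20 |
| Standard error of one mean at the enrolled 24 | 5/√24 = 1.02 | α, the two arms, and the effective size of 20 |
| 1.0 as a standardised effect, one-tailed t-test | power 69% at 10 per arm, 77% at 12 | SD 5 is unused and no power is stated |

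**What the planned size delivers, with SD 5.**

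| Quantity | 10 per arm | 12 per arm (all complete) |
|---|---|---|
| SE of the difference, 5·√(2/n) | 2.24 | 2.04 |
| One-sided 95% margin, z | 1.645 × 2.236 = 3.68 | 3.36 |
| One-sided 95% margin, t | 1.734 × 2.236 = 3.88 (18 df) | 3.51 (22 df) |
| Two-sided 95% CI half-width, t | 2.101 × 2.236 = 4.70 | 4.23 |

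The most lenient use of the 20 patients, pooling both arms as one mean, gives a standard error of 5/√20 = 1.12 and a one-sided margin of 1.84 (z) or 1.93 (t). Neither is 1.0, and a pooled mean says nothing about the effect of treatment. The mean of a single arm of 10 has a standard error of 5/√10 = 1.58.

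**The case against.** The strongest reply is that the plan never defines "a sampling error of 1.0" and never ties it to the difference between arms, so it makes no explicit promise about that difference. This stands in part. The near fourfold gap is specific to the margin reading applied to the difference; on the standard-error reading the gap is just over twofold. It does not rescue the 20, because no definition tried reaches it while using all three inputs. An undefined term in the only size justification is itself a defect.

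The near-match at 24 patients (5/√24 = 1.02) may be where the size came from. However, 24 is the number after the dropout allowance, α is unused and the arms are pooled. It is therefore not a derivation of an effective 20 for a two-arm comparison.

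Two further points are fair. The 3.9 is t-based while 68, 136 and 272 are z-based, so the method should be labelled; the effect is small (272 against 274 in total). Also, the Statistic analysis section names a chi-square comparison, which yields no margin on a difference in means. Restating the precision will not by itself connect the size to the analysis; that is a separate problem.

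Finally, because the size can stay, this could be seen as a disclosure correction of lesser weight. But it corrects a figure on which the whole size rests.

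**Conclusion.** The concern holds. The effective size of 20 is not reproduced by any reading examined that keeps the SD of 5, the one-tailed α of 0.05 and the 1.0 together. For the control versus experimental comparison, 10 per arm gives a one-sided 95% margin of 3.88 (t) or 3.68 (z), almost four times the stated 1.0, or a standard error of 2.24, more than twice it.

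That the figure cannot be reproduced rests on the plan's own inputs. The sizes of the shortfall assume in addition that 5 is the between-patient SD of the outcome compared, equal in both arms, with 10 evaluable patients in each. They apply only to that one outcome, and the plan does not say which of the nine measures it is.

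The two enrolment figures, 20 in Trial design and 24 in Sample size, also conflict. This looks like a wording slip between evaluable and enrolled numbers. The correction should be made before the plan is relied on.

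**What to change.** Keep the size and replace the sampling-error statement with the precision that it delivers, for example:

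> With 10 evaluable patients per arm and an SD of 5 for [the outcome this SD comes from], the between-group difference is estimated with a one-tailed 95% margin of about 3.9 (t-based; two-sided 95% CI half-width about 4.7).

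The sponsor must fill in the outcome and its unit. In Trial design, change the enrolment line to 24 patients enrolled (20 evaluable).

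If 1.0 is really needed, define sampling error and recalculate on that definition: 100 evaluable patients if it is the standard error of the difference, or 272 (z-based) if it is a one-sided margin of error on the difference, before the dropout allowance.

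The first option costs one sentence and one number and needs no extra patients; its drawback is that the stated precision becomes less favourable. The second multiplies the evaluable size by 5 (100/20) to 13.6 (272/20).

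### The sample size assumes a one-tailed 5% error, but the objective is non-directional and so is the named chi-square test

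*Combined protocol and SAP*

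**What the plan says.** All references are to the combined protocol and SAP.

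- **Sample size:** "We assumed an one-tailed α error of 0.05", together with "a sampling error of 1.0". The SD comes from an earlier study, "in which the standard deviation was 5"; the variable and its unit are not named. Enrolment is 24 (12 per arm), with 10% dropout allowed for and 20 effective. No power and no target between-group difference are given.
- **Study objectives:** the aim is to identify "whether applying GnRHa on patients with ovarian malignancy for fertility preservation surgery preoperatively and postoperatively has a different outcome".
- **Statistic analysis:** ovarian volume, six hormone indexes, AMH and the ovulating period are to be "compared by chi-square analysis in SPSS 17.0". The section gives no significance level, no sidedness and no one-sided form of the test.

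The one-tailed 0.05 is the only alpha in the document. No one-sided hypothesis is written, and no reason is given for a one-tailed level.

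**The concern.** A one-tailed level makes sense only when the direction of interest is fixed in advance for each outcome. Here it is fixed for none, and the analysis lists nine measures (1 volume + 6 hormones + AMH + ovulating period) without naming a primary one.

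This leaves the analyst two routes. One is to carry the one-tailed level into the analysis with no direction defined. That leaves room to choose the direction afterwards, and a one-tailed test for benefit could not declare a worsening of ovarian function, although a worsening would also be a different outcome. The other is to take the usual chi-square p-value at 0.05. The test is then two-sided and the planning assumption no longer applies. A reader cannot tell which is meant.

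**Working it through.** **Inputs.** From Sample size: SD 5, sampling error 1.0, one-tailed alpha 0.05, 12 per arm enrolled, 10% dropout, 20 effective (10 per arm). Power is not stated; 80% is assumed where a formula needs it.

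**1. The plan's own figure.** The dropout step reproduces when it is done per arm: 10 / 0.90 = 11.1, rounded up to 12, so 24 in total. The 20 does not reproduce from the stated one-tailed inputs (step 4).

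**2. Error rate against test.**
- Chi-square, 1 df, 0.05: cut-off 3.841 = 1.960², the two-sided z test.
- One-tailed 0.05: 1.645² = 2.706, which is the chi-square cut-off at 0.10 with the direction then checked.
- With more than 1 df, the chi-square statistic has no direction at all.

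**3. Precision that 10 per arm delivers for a difference in means.**
- Standard error = 5 × √(2/10) = 2.236.
- One-sided margin: t(0.95, 18 df) × SE = 1.734 × 2.236 = 3.88.
- Two-sided half-width: t(0.975, 18 df) × SE = 2.101 × 2.236 = 4.70.

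Both are several times the stated 1.0.

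**4. Effect of sidedness on the number required.** The phrase "a sampling error of 1.0" does not say what the error refers to, so three readings are shown.

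| Reading of 1.0 | Formula | One-sided | Two-sided |
|---|---|---|---|
| Margin for a single-group mean | (z × 5 / 1)² | 67.6 → 68 | 96.04 → 97 |
| Margin for a difference, per arm | 2 × (z × 5 / 1)² | 135.3 → 136 | 192.1 → 193 |
| Target difference, assumed 80% power, per arm | 2 × (z + 0.842)² × 25 / 1² | 309.3 → 310 | 392.6 → 393 |

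Here z is 1.645 one-sided and 1.960 two-sided. No cell gives 20 or 24.

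**5. Near matches.** Two come close, but each departs from the stated inputs. Treating 5 as a variance with a two-sided z gives 1.960² × 5 = 19.2, rounded up to 20; the one-tailed z gives 13.5, rounded up to 14. Treating 1.0 as a standard error gives (5/1)² = 25 and uses no alpha. The planned number therefore cannot be traced to the one-tailed level.

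**The case against.** **The title mentions protection, so a direction is implied.** It hints at what the investigators expect. A title is not a hypothesis, though, and the written objective has no direction.

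**A one-sided version of chi-square exists for a 2×2 table.** It does, as the signed square root. The plan does not specify it, or a direction for it.

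**The analysis section sets no alpha, so nothing conflicts.** This stands in part. The one-tailed level appears only in the sample-size reasoning. If chi-square is run in the usual way at 0.05, each comparison has a nominal two-sided 5% level and nothing doubles. A reader might infer that the trial will run at a 10% false-positive rate. The documents do not support that: it needs both a one-tailed analysis and a direction chosen after seeing the data, and neither is written.

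**Sidedness has no traceable effect on the planned number.** This stands. A reader might also infer that the error costs a definite number of patients, such as 136 rising to 193 per arm. That is one of several readings of an undefined term.

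**The larger defects lie elsewhere.** This is fair. Power and target difference are missing, and chi-square does not suit measured quantities such as volume, hormone levels and AMH. These are separate problems and do not remove this one.

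**Conclusion.** The inconsistency is real. The only alpha in the document is one-tailed 0.05, while the objective and the named test are both non-directional. It is a mismatch in the planning assumption, not evidence of an inflated error rate in the analysis.

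Its firm size is in the precision: about 4.7 two-sided against 3.9 one-sided, assuming SD 5 applies to the outcome analysed, 10 per arm are evaluable and means are compared. Its effect on the required number ranges from 68 to 97 (single group) up to 310 to 393 per arm (target difference, assumed 80% power). Because 20 and 24 fail even one-sided under all three readings, correcting the sidedness alone does not repair the sample size.

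**What to change.** 1. In Sample size, change the alpha to two-sided 0.05.
2. In Statistic analysis, state that between-group comparisons are two-sided at 0.05 with 95% confidence intervals. For the measured outcomes, take the intervals from a comparison of means, since chi-square does not provide them.
3. Restate the precision: with SD 5 and 10 per arm, a half-width of about 4.7 for a difference in means, in place of 1.0. Name the variable to which the SD belongs.
4. State that these changes correct the error rate and the precision and do not justify 20 or 24. That justification needs a primary endpoint, a target difference, a power and a fresh calculation.

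A one-sided level would also be coherent, provided the sponsor justifies it and fixes the direction for each outcome in advance.

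Items 1 and 2 are wording changes, apart from naming a comparison of means for the measured outcomes. Item 3 adds a short calculation and shows a less favourable precision than the plan now implies. None changes enrolment by itself; the recalculation in item 4 is separate work and could.
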